2.2 Justification for the research

The P3-BBnet design offers a safe and affordable method to extend LLIN lifespan in the fight against malaria. Entomological results in laboratory and field experimental hut trials have shown the promise of P3-BBnets but this will the first epidemiological test of their effectiveness. Embedding the trial into a programmatic distribution of 300,000 P3-BBnets alongside a much larger distribution of PermaNet 3, coupled with ANC-based monitoring of malaria prevalence, provides an efficient and cost-effective pragmatic methodology for the trial.

2.3 Study setting

Haut Katanga is a south-western province of DRC with a population of approximately 7.5 million people (2021 data), within an area of approximately 132,500 km². The largest city is Lubumbashi, the second largest city in DRC, with a 2015 population estimate of around 1.8 million people. Haut Katanga has 27 health zones; these are subdivided into a total of 359 health areas (median per zone=15; range=6-20). Health zones are organised into five supervision axes: Lubumbashi (13 zones); Likasi (5 zones); Pweto (5 zones); Mitwaba (3 zones) and Sakania (1 zone). Pyrethroid resistance data (*An. gambiae s.l.*) for the province suggest moderate-high prevalence to deltamethrin (and other pyrethroids, not shown), which is quite well blocked by the synergist PBO (Fig. 3); a constituent of PermaNet 3 and P3-BBnets. Total malaria case rates (approximated as total cases/ health zone population) are moderately seasonal across Haut Katanga's health zones, with approximately twofold variation across the year, and only slightly lower estimated case rates within Lubumbashi's health zones (Fig. 4). Owing to this comparability, and to reduce logistical demands arising from poor

transport links, the trial will focus on health zones in Lubumbashi, in which the density of health areas is highest permitting access to many health areas on a limited geographical scale. In addition, the greater expected robustness of household walls in more urban, compared to rural, settings

Figure 3. Insecticide resistance bioassay data for the pyrethroid insecticide deltamethrin with and without the synergist PBO from the PMI-Vectorlink programme. Haut Katanga results are highlighted.

should aid consistent placement of the hooks provided to hang the barrier of the P3-BBnets.

2.4 Sample size

Projected sample size requirements for the number of clusters required were evaluated under two designs, the first with equal numbers of P3-BBnet and PermaNet 3 clusters monitored and the

second with a ratio of 0.5 (P3-Bbnet/ PermaNet 3), reflecting the more limited numbers of BBnets available. This second imbalanced design proved more feasible to provide suitable power and is presented. Calculations are applied with required power = 80%; type I error rate = 0.05; coefficient of variation for clustering of 0.30 (approximating that observed in the Sud Ubangi trial). We assume that 25 ANC1 visitors will be recruited on average per month per cluster. A single monitoring periods of 3 consecutive months is planned, giving an average cluster size of at least N=75.

Estimated numbers of clusters for a two-sample proportions test	Compute:	* Accepts numlist (
Cluster randomized design, Pearson's chi-squared test	Group-specific numbers of clusters	
Ho: p2 = p1 versus Ha: p2 != p1	Error probabilities	
	0.05 * Significance level	0.8 * Power ~
Study parameters:		
	Clusters	
alpha = 0.0500	Specify the ratio of the numbers of clusters:	Specify cluster sizes/sample sizes:
power = 0.8000	0.5 * Ratio, K2/K1	Group cluster size and ratio \sim
delta = -0.0000 (difference)		75
$p_1 = 0.2400$ $p_2 = 0.1800$		75 × Control ~
		1 * Ratio, M2/M1
Cluster design:	Allow fractional numbers of clusters and sample sizes	;
$k_{ratio} = 0.5000$	Effect size	
M1 = 75	Proportions	Report effect size as:
M2 = 75	0.24 * Control	Difference
rho = 0.0250		Difference
	0.18 * Experimental ~	0.025 * Intraclass correlation
Estimated numbers of clusters and sample sizes:		
V1 - 1 2	Specify varying cluster sizes	
$K_1 = 42$ $K_2 = 21$	* Coefficient of variation for clus	ter sizes
N1 = 3.150		
N2 = 1,575	Cide a	
	Sides:	
	Iwo-sided test	
	Treat number lists in starred(*) options as parallel	

Figure 5. Screenshot from Stata showing sample size calculation for the primary endpoint (malaria prevalence at ANC1s).

The base malaria prevalence for Haut Katanga is taken from available malaria indicator survey (MICS) data (Fig. 2), which in Sud Ubangi corresponded closely with the ANC1 rate we observed in the PermaNet 2 arm. In the Sud Ubangi trial analysis, clusters receiving PermaNet 3 exhibited up to 30% lower prevalence than those receiving standard nets. This is assumed to represent the expected effect size for PermaNet 3, i.e. they will act to reduce malaria prevalence by 30% compared to the prevalence rate of 34% from the MICS (Fig. 2). Sample size calculations are based on a projected *additional* effect of P3-BBnets vs P3 of 25%. Therefore, the prevalence projected in each study arm is PermaNet 3 = 0.24 and BBnet = 0.18. The sample size calculation performed in Stata is shown in Fig. 5 and suggests that with these parameters 21 P3-BBnet clusters and 42 PermaNet 3 clusters are required.

2.5. Cluster allocation and bednet distribution

Health areas from within the designated study health zones which have a functional ANC receiving on average ≥25 ANC1 visitors/month (based on DHIS2 data from September 2021-August 2022), form the list from which clusters were randomly-chosen. We will include all the health areas to which P3-BBnets are distributed as clusters for ANC1 monitoring and twice this number of PermaNet 3 clusters, chosen at random from within the same health zones.

Nine Lubumbashi health zones are identified (Fig. 6), which are wholly within Lubumbashi (this excludes Kipushi and Kafubu), and do not have military encampments (this excludes Kowe and Vangu). Within these nine health zones, health areas will by default receive PermaNet 3 unless randomly chosen to receive P3-BBnets. Table 1 shows the nine health zones including estimated projections of net need. In total, 133 health areas were identified (within the nine health zones)

which receive on average ≥25 ANC1 visitors per month and these were included in the list for allocation to be clusters in the study. Using a random number generator, 30 health areas were chosen, of which the first 21 were proposed for coverage by BBnets, with the additional health areas (random numbers 22-30 in order) serving as additions if sufficient P3-BBnets remain after distribution to the first 21, or as backups in case ANCs in any areas are no longer fully-functional or health centres do not wish to participate. The randomised choice was made by a non-study team member and was communicated to the SANRU distribution team.

Distribution of nets occurred under the standard procedures of the PNLP and SANRU distribution programme, which delivers bednets to health areas for distribution by community health workers. Based on the randomised allocation, each health area received bales of the appropriate bednet for onward distribution to households. Bednets are not routinely distributed with hanging materials, but for the P3-BBnets, string and hooks were provided (by the study team) to promote suspension of the barrier. Community health workers were trained to advise householders on the function of the barrier, its potential advantage and how to suspend it. If the householder decides not to suspend the barrier, the P3-BBnet will still provide protection in the same way as a PermaNet 3, given the identical physical and chemical composition of the net material.

Figure 6. Map of Haut Katanga showing the 27 health areas. Inset shows enlargement within Lubumbashi city. Triangles show the nine health zones included for BBnet random allocation to health areas.

Table 1. Health zones (HZ) within Lubumbashi included in the list for inclusion, with information on the number of health areas and estimates for net need. The right column shows the random choices with the number of health areas that will be covered by Bbnets in the study, allowing for uncertainty in net need estimates. The final distribution list may differ slightly depending on logistical constraints

Possible HZ	Total HA (N=133)	HA (N=21)		
Kamalondo	2	0		
Kampemba	21	2		
Katuba	6	0		
Kenya	16	1		
Kisanga	15	0		
Lubumbashi	17	4		
Mumbunda	17	4		
Ruashi	25	6		
Tshamilemba	14	4		
Net need estimate				
lower	1704110	275531		
upper	1917124	309972		

Note added in V2.2: the final distribution was to 63 health areas as planned but these spanned 7 health zones rather than 9 (see Appendix G).

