Appendix G. Clusters to which nets were distributed

				Healt zones
cluster	ZDS	ADS	Net type	(where grouped)
				Ruashi-
1	Ruashi	Kijiba	BB nets	Kampemba Ruashi-
2	Ruashi	Kikunda	BB nets	Kampemba Ruashi-
3	Ruashi	Mukulu	BB nets	Kampemba
4	Ruashi	Kamasaka	BB nets	Kuashi- Kampemba
5	Ruashi	Kawama	BB nets	Kuashi- Kampemba
6	Ruashi	Kalukuluku	BB nets	Kuashi- Kampemba
7	Ruashi	Kizanga	BB nets	Ruashi- Kampemba Ruashi
Q	Ruashi	ا م //عالمم	BB nots	Kudsill- Kampemba
0 0	Lubumbashi	Tingi tingi	BB nots	Lubumbashi
10	Lubumbashi	Kacana 1	DD Hets	Lubumbashi
10	Lubumbashi	казара т	DD HELS	Lubumbashi Puachi
11	Kampemba	Safina	RR nots	Kampemba
TT	Kampemba	Sallia	DD HELS	Rupshi
12	Kampemba	Triangle	R B nets	Kampemba
12	Tshamilemha	Ciment Kat	BB nots	Tshamilemha
1/	Tshamilemba	Eoire	BB nots	Tshamilemba
14	Tshamilomba	Kigoma Quast	DD Hets	Tshamilemba
15	Konya		DD Hels	Konyo
10	Kenya	CASUP	BB nets	Kenya
1/	Kenya Nawa kuwa da		BB nets	Kenya Nawalawa da
18	Mumbunda	Plateau 1	BB nets	Mumbunda
19	Mumbunda	Maisha	BB nets	Mumbunda
20	Mumbunda	Salama	BB nets	Mumbunda
21	Kisanga	Wantanshi	BB nets	Kisanga Ruashi-
22	Ruashi	Baraka	P3 nets	Kampemba Ruashi-
23	Ruashi	Telecel	P3 nets	Kampemba Buashi-
24	Ruashi	Congo 2	P3 nets	Kampemba Ruashi-
25	Ruashi	Shindaika	P3 nets	Kampemba
26	Ruashi	Bendera	P3 nets	Kampemba Ruashi-
27	Ruashi	Congo 1	P3 nets	Kampemba Ruashi-
28	Ruashi	Luwowoshi	P3 nets	Kampemba
29	Ruashi	Neo Apostolique	P3 nets	Ruashi-

				Kampemba
				Ruashi-
30	Ruashi	Orphelinat	P3 nets	Kampemba Ruashi-
31	Ruashi	Orthodoxe	P3 nets	Kampemba
32	Lubumbashi	Kiwele	P3 nets	Lubumbashi
33	Lubumbashi	Gambela 2	P3 nets	Lubumbashi
34	Lubumbashi	Kalubwe 1	P3 nets	Lubumbashi
35	Lubumbashi	Kamatete	P3 nets	Lubumbashi Ruashi-
36	Kampemba	Cité de Jeunes	P3 nets	Kampemba Ruashi-
37	Kampemba	ECASET	P3 nets	Kampemba Ruashi-
38	Kampemba	Emmaûs	P3 nets	Kampemba Ruashi-
39	Kampemba	Kabanga	P3 nets	Kampemba Ruashi-
40	Kampemba	Kamasaka	P3 nets	Kampemba Ruashi-
41	Kampemba	Lapofa	P3 nets	Kampemba Ruashi-
42	Kampemba	Mubindu	P3 nets	Kampemba Ruashi-
43	Kampemba	Njanja	P3 nets	Kampemba Ruashi-
44	Kampemba	Sab	P3 nets	Kampemba Ruashi-
45	Kampemba	Suzanella	P3 nets	Kampemba
46	Tshamilemba	Hewa Bora 2	P3 nets	Tshamilemba
47	Tshamilemba	Rail	P3 nets	Tshamilemba
48	Tshamilemba	Agetraf	P3 nets	Tshamilemba
49	Tshamilemba	Kigoma Est	P3 nets	Tshamilemba
50	Tshamilemba	Kinsense Quartier	P3 nets	Tshamilemba
51	Tshamilemba	Industriel	P3 nets	Tshamilemba
52	Kenya	Lubumbashi	P3 nets	Kenya

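### At least 4 of the 21 health areas first drawn for BBnets were replaced without this being disclosed, and the enrolment rule does not keep displaced areas out of the PermaNet 3 arm

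*Protocol*

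**What the plan says.** Section 2.5 describes a random list: "30 health areas were chosen, of which the first 21 were proposed for coverage by BBnets". Numbers 22 to 30 are held in order, either as additions if nets remain or "as backups in case ANCs in any areas are no longer fully-functional or health centres do not wish to participate". Someone outside the study team made the draw.

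The caption of Table 1 identifies its N=21 column as the outcome of that draw: "The right column shows the random choices with the number of health areas that will be covered by Bbnets in the study". It adds a caveat: "The final distribution list may differ slightly depending on logistical constraints". A note added in v2.2 states that "the final distribution was to 63 health areas as planned but these spanned 7 health zones rather than 9" and points to Appendix G, which lists 21 BBnet and 42 PermaNet 3 clusters by zone and area.

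On enrolment, section 2.5 takes every area that was supplied with BBnets as a BBnet cluster, and areas not chosen for BBnets get PermaNet 3 by default. Section 2.5.1 picks controls at random among the PermaNet 3 areas of the same zone, after the distributor has reported where the BBnets went. Section 5.1 names ITT and per-protocol analyses in connection with women who attend outside their own area. It does not say whether a cluster's arm is the one drawn or the net delivered.

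**The concern.** In a cluster trial the protection of randomisation attaches to the areas as drawn. If areas drawn for BBnets were dropped and others put in, the reader needs to know which ones, why, and whether the substitutes came from the reserve list in order. The reasons the protocol foresees (clinic function, refusal, logistics) could be related to malaria prevalence, and they act only on the BBnet side.

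Controls are drawn after distribution from whatever areas received PermaNet 3. An area that was randomised to BBnets but lost them therefore sits in the control pool. Following section 2.5.1 as written, it can be monitored and analysed as a PermaNet 3 cluster, which is the opposite of its random allocation.

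**Working it through.** **Inputs.** BBnet areas by zone from Table 1 (random choices) and Appendix G (delivered); eligible areas by zone from Table 1; PermaNet 3 clusters by zone from Appendix G; prevalences 0.24 and 0.18, intraclass correlation 0.025, cluster size 75 and coefficient of variation 0.30 from section 2.4.

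**1. The protocol's own sample size.** Two-sided 5% test, 80% power, ratio 0.5: 1,098 women in the control arm before clustering. Design effect = 1 + 74 × 0.025 = 2.85. Control clusters = 1,098 × 2.85 / 75 = 41.7, so 42; BBnet clusters 20.9, so 21. Power at 42 v 21 is 80.3%. The stated figure is reproduced.

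**2. Minimum number of replaced areas.**

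| Zone | Eligible | BBnet, Table 1 | BBnet, App. G | Change | PermaNet 3, App. G |
|---|---|---|---|---|---|
| Ruashi | 25 | 6 | 8 | +2 | 10 |
| Kenya | 16 | 1 | 2 | +1 | 4 |
| Kisanga | 15 | 0 | 1 | +1 | 2 |
| Kampemba | 21 | 2 | 2 | 0 | 10 |
| Lubumbashi | 17 | 4 | 2 | -2 | 4 |
| Mumbunda | 17 | 4 | 3 | -1 | 6 |
| Tshamilemba | 14 | 4 | 3 | -1 | 6 |
| Kamalondo, Katuba | 2, 6 | 0, 0 | 0, 0 | 0 | 0, 0 |
| Total | 133 | 21 | 21 | +4, -4 | 42 |

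The largest possible overlap is the sum over zones of the smaller count: 6 + 1 + 0 + 2 + 2 + 3 + 3 = 17. At least 21 - 17 = 4 areas (4/21 = 19%) were replaced; swaps within a zone would add to this. Grouping Ruashi with Kampemba, as Appendix G does, changes 8 to 10 and still gives 4.

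**3. What the note discloses.** Table 1's 21 choices have non-zero counts in six zones, and Appendix G has seven. Moving from nine candidate zones to seven therefore says nothing about the exchange of BBnet areas.

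**4. Controls follow the net delivered.** In Lubumbashi, Appendix G has 4 controls, twice the 2 BBnet areas delivered, not twice the 4 drawn. Kenya, Kisanga, Mumbunda and Tshamilemba also show exactly 2:1 on delivered areas. Ruashi (10:8) and Kampemba (10:2) meet 2:1 only when grouped (20:10).

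**5. Chance that a displaced area re-enters as a control.** Assume the minimum of 4 displaced areas, all still eligible, and simple random choice of controls within the zone.

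- Lubumbashi: 17 - 2 = 15 candidates, 4 chosen, 2 displaced. P(neither) = C(13,4)/C(15,4) = 0.524.
- Mumbunda: 14 candidates, 6 chosen, 1 displaced. P(not chosen) = 8/14 = 0.571.
- Tshamilemba: 11 candidates, 6 chosen, 1 displaced. P(not chosen) = 5/11 = 0.455.

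P(at least one) = 1 - 0.524 × 0.571 × 0.455 = 0.86. Expected number = 2 × 4/15 + 6/14 + 6/11 = 1.5.

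**6. Possible bias, as a range.** If substitutes and displaced areas differ in underlying prevalence by d points, the BBnet arm mean shifts by d × 4/21. For d = 2, 5 and 10 (assumed values) this is 0.4, 1.0 and 1.9 points, or 6%, 16% and 32% of the planned 6-point difference. For scale, the protocol's coefficient of variation gives a between-cluster SD of 0.30 × 24 = 7.2 points. The chance SD of a difference between two means of 4 areas is then 7.2 × √(1/4 + 1/4) = 5.1 points, so d = 10 is about 2 SD. The direction is unknown.

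**7. Power of alternative analysis sets** (protocol's prevalences and intraclass correlation).

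- Retained draws only, at most 17 v 42: about 74%.
- All 21 first-drawn areas kept as BBnet, 4 of them having received PermaNet 3: expected prevalence (17 × 0.18 + 4 × 0.24)/21 = 0.191; power about 61%.
- One cluster lost from each arm, 41 v 20: 78.6%.

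**The case against.** The strongest reply is that ranks 22 to 30 were drawn at random in advance by someone outside the team. If they replaced earlier ranks in order, for reasons unrelated to outcome, the delivered BBnet set still comes from the random list, including the area in Kisanga. This stands. A reader might infer from the zone counts that the BBnet arm does not follow the randomisation; the document does not confirm or exclude that, so the departure is unverified, not proven.

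Other stronger readings also fail:

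- **The note is false.** Its statement about 63 areas is correct (21 + 42), and Table 1 warned of small departures. The note is incomplete. However, the logistics caveat is not one of the reasons for which section 2.5 allows a backup.
- **A displaced area is in fact a control.** This is possible but not documented. An area dropped because its clinic closed or refused would be unlikely to be monitored, so the 86% is conditional on continued eligibility.
- **ITT here means nets delivered.** Section 5.1 does not define ITT at cluster level, and a statistical analysis plan may do so. It would still need the draw order, and the selection rule that admits displaced areas is in the protocol itself.
- **Kamasaka is one area in both arms.** Cluster 4 is listed under Ruashi and cluster 40 under Kampemba; they may be two areas with the same name. If so, the ambiguity affects only women who attend elsewhere and name that area in Q1.6 of Appendix E, and Q1.4 also records their village.
- **Ruashi's rise from 6 to 8 shows steered substitution.** Singling out the most extreme zone after seeing the data is not evidence of this.

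**Conclusion.** The point holds in this form. At least 4 of the 21 first-drawn BBnet areas (19%) were replaced; this rests only on reading Table 1's column as its caption describes it. The v2.2 note does not disclose it, and nothing shows whether the substitutes were ranks 22 to 30 in order for the permitted reasons. As written, sections 2.5 and 2.5.1 also allow an area randomised to BBnets to be analysed as a control.

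The effect on the result cannot be determined from the protocol. It could be nil if the reserve list was followed for unrelated reasons, or up to about a third of the planned difference under a deliberately large assumed gap. As it stands, allocation cannot be verified for about a fifth of the intervention arm, and this should be settled before arm codes are linked to outcomes.

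**What to change.** 1. Correct the v2.2 note, and add to Appendix G each area's random rank (1 to 30), the reason for each substitution, and the fate of each displaced area (net received, monitored or not).
2. State in sections 2.5.1 and 5.1 that the cluster-level ITT arm follows the ranked random list, with backups counted as BBnet where the section 2.5 rule was followed, and that an area ranked 1 to 21 that did not receive BBnets is not analysed as a PermaNet 3 control.
3. Add a sensitivity analysis restricted to areas delivered as ranked. With at most 17 v 42 clusters and about 74% power it is supportive only.
4. Establish whether Kamasaka is one area or two. If one, drop it from both arms. If two, use village (Q1.4) and health zone to assign women who attend elsewhere.

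The cost is document work from a list that already exists, plus one extra analysis. Excluding any displaced area found among the controls would lose that control cluster. Dropping Kamasaka from both arms would cost about 1.7 points of power (80.3% to 78.6%). None of the steps needs new data collection, which matters because v2.2 is dated at or near the end of the monitoring window.

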2.5.1 Health area enrolment

It is planned that all health areas receiving P3-BBnets will be enrolled into the study. Twice the number of health areas that received PermaNet 3 within a specific health zone that is receiving P3-BBnets will be randomly chosen to be enrolled for monitoring in the study. Thus, for example in Kenya health zone (Table 1), which has one P3-BBnet area proposed for inclusion in the study, two PermaNet 3 health areas would be chosen at random from the remaining 15 for inclusion for monitoring. The final decision on PermaNet 3 health areas are chosen will be taken once the final report of the distribution of P3-BBnet locations is received from SANRU. Health centres will be contacted following liaison with the provincial health director followed by medical chiefs of each health zone for involvement in the study. The primary contact point for the study in each health centre will be the nurse responsible for running ante-natal clinics, who will be responsible for recruitment of visitors to the trial.

2.5.2 Training

Training will follow the same model as applied successfully in the trial in Sud Ubangi province. Nurses at health centres responsible for the enrolment of participants into the study will be trained in workshops organized by the KSPH team, in coordination with the PNLP focal point. Training will be provided in ethical recruitment procedures and safeguarding, completion of questionnaires, and data entry into phones (provided by the study team). Given the relatively small geographical scale of the study area, it is feasible that all training may be conducted centrally in one or two one-day workshops.

3. Recruitment

3.1 ANC clinic visitors

The recruitment process at each clinic will occur when women attend their first ANC appointment (scheduled for the second trimester, though in our experience some women attend late). Women will be asked if they would like to be enrolled in the study, the main implication of which for them is

to take an RDT test for malaria (Fig. 7) and to answer a short questionnaire, which should take no more than 15 minutes. Women are given information as soon as they arrive at the clinic and have time to consider until the time of their scheduled appointment. It will be made clear that there is no direct benefit to participation, and that the results are to help evaluate different bednets distributed as part of the provincial programme. If, after asking any questions and discussing with friends or relatives as desired, they agree and sign the consent form, the questionnaire will be administered by health centre staff and the malaria test result added to this form. The form will include no personally-identifiable data. The decision to participate or not will need to be taken within the timeframe of the appointment. The information leaflet and consent form are provided in **Appendix A**.

Figure 7. Recruitment and testing protocol for the trial (identical to that implemented in Sud Ubangi 2020-2022). Adapted from an original protocol applied in DRC by MSF (Hellewell et al 2018)

3.2 Household surveys

Following initial contact with community leaders facilitated by health centre staff, boundaries of the health areas will be mapped to delimit the area to be surveyed (and the GPS coordinates of each centre holding an ANC clinic will be recorded). Households within the health area will be visited by study personnel, accompanied by a local resident, typically a member of the community health worker's team. From a starting point, a first house will be chosen and subsequent houses sampled based on separation by approximately 50m. If householders are present, the purpose of the study and nature of the request for participation will be explained to them, and if they are willing to be enrolled the head of the household will be asked to sign a consent form, which will give permission (subject to verbal consent at the time of collection) to visit the house to conduct questionnaires of net use and perceptions. Prospective participants will be given up to 24 hours to decide whether to take part. If they do not wish to take part, or the head of the household), a neighbouring house will be approached. The questionnaire will be taken, and net hanging observed, including the position of barriers in houses with P3-BBnets. A photograph of bednets hanging *in situ*, excluding any people, may be taken subject to specific consent from the householder. An equal

number of P3-BBnet and PermaNet 3 houses will be surveyed. The information leaflet and consent form is provided in **Appendix B**. A total of approximately 200 houses will be sampled.

